8.11 Caliper Measurements

Caliper measurements of submental fat thickness will be taken at screening and at study visits Day 28, Day 56 and Day 84.

To make the measurement, the subject's head should be maintained in a neutral position and the caliper positioned to pinch the skin at 15 mm on either side of the center point of the submental area.

The change from baseline in caliper-measured submental thickness will be calculated as an exploratory efficacy endpoint.

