Study Procedure	Screening Day	Baseline (Treatment)	Visit Schedule (Days 1 to 84)				
Study Day	Day (-28) through Day (-1)	Day 0	Day 1	Day 7	Day 28	Day 56	Day 84
Signed informed consent	Х						
Medical history	Х						
Physical Exam	Х		Х	X			Х
Concomitant Medication	X	Х	Х	Х	Х	Х	Х
Pregnancy β-hCG	Х						
Pregnancy urine test (women)		Х					X
Caliper measurement of submental fat	X				Х	X	Х
Weight measurements	Х	Х			Х	Х	Х
Biochemistry Lab parameters	Х		Х	Х	Х		X
Pharmacokinetics		Х	Х				
ECG	X		Х				Х
Vital signs	Х	Pre X post	Х	X	Х	Х	Х
Injection of RZL- 012		Х					

Medi Stat	DOCUMENT	NUMBER: 140-1	BST-PLN-00	1	PAGE	: 12 of 2	20	
TITLE: Statistical Analysis Plan	of Protocol Numb	per RZL-012-SMF(C-P2US-001				ATE: 03/0 ABER: 1.0	
Clinician Chin Assessment Tool (C-CAT)	X	X			X	Х	X	
Subject- Self-Chin Assessment Tool (S-CAT)	X	x			X	X	X	
Physician Global Assessment Improvement Scale (GAIS) and physician global assessment	X				X	X	X	
Subject's Satisfaction questionnaire for SMF appearance	X				Х	Х	Х	
Subject's impact questionnaire	X				Х	Х	Х	
Subject Global Assessment of Change and subject self assessment	X				Х	Х	х	
2D Standardized photography	X		Х	X	Х	Х	Х	

Х

Х

Х

Х

Х

AEs

Х

Medi Stat	DOCUMENT NUMBER: 140-BST-PLN-001	page: 13 of 20
TITLE: Statistical Analysis Plan	of Protocol Number RZL-012-SMFC-P2US-001	EFFECTIVE DATE : 03/08/2022 REVISION NUMBER : 1.0

• Rationale Sample Size Calculation

20 adult volunteers (10 Chinese and 10 non-Chinese) whose age is within 18 to 65 years who have consented to participate in this study and seek submental fat reduction will be enrolled into the study.

No formal sample size calculation was performed. The planned sample size of 10 subjects per study arm is sufficient to compare the PK profile between the 2 study populations. Any p-value which may be shown in the final report, will be presented only to establish trends.

• Statistical Analysis Software and Data Management

Data manipulation, tabulation of descriptive statistics, calculation of inferential statistics, and graphical representations will be performed using SAS® version 9.4 or higher for Windows. If the use of other software is warranted, the final statistical methodology report will detail what software was used for what purposes.

• Data Management

Data management for the study is performed by Medistat.

Medical Coding

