6. STATISTICAL ANALYSIS

• General

All measured variables and derived parameters will be listed individually and, if appropriate, tabulated by descriptive statistics.

For categorical variables, summary tables will be provided giving sample size, absolute and relative frequency by study group. Confidence intervals (95% degree of confidence) for proportions will be presented for selected endpoints.

For continuous variables, summary tables will be provided giving sample size, arithmetic mean, standard deviation, coefficient of variation (CV%), median, minimum and maximum and 95% CI (Confidence Interval) for means of variables by study group.

All tests will be two-tailed, and a p value of 5% or less will be considered statistically significant.

The data will be analyzed using the SAS ® version 9.4 (SAS Institute, Cary North Carolina).

Statistical methods presented in the SAP may be slightly different from those that are presented in the protocol. Differences are clearly stated and the SAP supersedes the protocol only with regard to the way data will be handled and analysed.

• Subject Disposition

A detailed description of subject accountability including count of subjects included, exposed, completed (i.e., subjects who complete the study treatment) and discontinued along with the main reason for discontinuation will be generated for each study arm (Chinese vs. non-Chinese) and for all subjects. All withdrawals from the study will be fully documented in the body of the Clinical Study Report.

Medi Stat	DOCUMENT NUMBER: 140-BST-PLN-001	page: 15 of 20
TITLE: Statistical Analysis Plan	of Protocol Number RZL-012-SMFC-P2US-001	EFFECTIVE DATE : 03/08/2022 REVISION NUMBER : 1.0

• Demographic and Baseline Characteristics

Baseline will be defined as the last available and evaluable parameter value before and closest to the injection. If a rechecked value is used for baseline, it should be collected under the same conditions as for the planned baseline.

Baseline data including demographics, weight, height, BMI, prior medications, medical history and pregnancy tests will be listed and tabulated with the appropriate descriptive statistics by study arm and for all subjects in ITT population.

Baseline safety data such as vital signs, ECG, safety laboratory assessments and physical examination will be presented along with subsequent safety values assessed during or after injections.

- Analysis of Primary Endpoint

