A two-sided test of equality of binomial proportions will be applied for testing the statistical significance of the difference in percent of subject who have at least a 2-grade improvement in both the C-CAT and S-CAT on Day 84 versus baseline.

• SMF thickness measured with caliper will be summarized by study visit (Screening, Day 28, Day 56, Day 84) and by study arm using continuous descriptive statistics. Change and relative change from baseline will be calculated and tabulated in the same manner.

The Paired T-test or Signed rank test for two means (paired observations) (as is appropriate) will be applied for testing the statistical significance of the reduction (change and relative change from baseline) in SMF thickness measured with caliper (Day 84 versus baseline) in each study arm.

The two-sample T-test or Non-parametric Wilcoxon-Mann-Whitney Rank sum test for independent samples (as is appropriate) will be applied for testing the statistical significance of the difference in reduction in SMF thickness measured with caliper (Day 84 versus baseline) between Chinese population and non-Chinese population.

Medi Stat	document number: 140-BST-PLN-001	page: 19 of 20
TITLE: Statistical Analysis Plan	of Protocol Number RZL-012-SMFC-P2US-001	EFFECTIVE DATE : 03/08/2022 REVISION NUMBER : 1.0

The additional exploratory endpoints will be analyzed as follows:

The SMF improvement using the Global Aesthetic Improvement Scale (GAIS), the physician Global Assessment of Change Scale, Subjects Global Self-Assessment of Change Scale, Subject's Global Assessment of Change Scale, the subject's satisfaction questionnaires, and the subject's impact questionnaire will be summarized at each timepoint and by study group.

• The physician global assessment will be summarized using categorical descriptive statistics by study visit for each study arm. Shift from baseline will be evaluated and tabulated in the same manner.

• The Physician Global Assessment Improvement Scale (GAIS) will be summarized using categorical descriptive statistics by study visit for each study arm.

• The Subject Global Self-Assessment scale will be summarized using categorical descriptive statistics by study visit for each study arm. Shift from baseline will be evaluated and tabulated in the same manner.

• The Subject Global Assessment of Change Scale will be summarized using categorical descriptive statistics by study visit for each study arm.

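### The between-arm caliper comparison uses change from baseline with no baseline-adjusted estimate beside it

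*SAP*

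**What the plan says.** The variable tested between arms is "the difference in reduction in SMF thickness measured with caliper (Day 84 versus baseline) between Chinese population and non-Chinese population" (SAP section 6, Analysis of Efficacy Endpoints). The test is set out as follows: "The two-sample T-test or Non-parametric Wilcoxon-Mann-Whitney Rank sum test for independent samples (as is appropriate) will be applied". The same paragraph summarises thickness by visit and by arm, and adds: "Change and relative change from baseline will be calculated and tabulated in the same manner".

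Baseline is defined in SAP section 6, Demographic and Baseline Characteristics: "Baseline will be defined as the last available and evaluable parameter value before and closest to the injection". Protocol 8.11 fixes when the caliper is used: "Caliper measurements of submental fat thickness will be taken at screening and at study visits Day 28, Day 56 and Day 84". For this endpoint, baseline is therefore the screening value.

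Neither document includes a model with baseline thickness as a covariate, or any other adjustment of this comparison. Neither specifies a confidence interval for the difference between arms; the intervals promised are for means by study group. The within-arm tests name both absolute and relative change, while the between-arm test speaks only of reduction.

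The arms are ethnic groups of 10 who all receive the same open-label treatment. Caliper reduction is a secondary objective (Protocol 3.1.2) and an exploratory endpoint (Protocol 3.2.2 and 8.11). The SAP's sample size paragraph says that p-values are shown only to indicate trends, while section 6 also says: "All tests will be two-tailed, and a p value of 5% or less will be considered statistically significant".

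**The concern.** Subtracting baseline removes its influence only if Day 84 thickness rises one-for-one with baseline. If the slope is below 1, as when extreme values regress towards the mean, thicker subjects show larger reductions whatever their population. An arm that starts thicker will then appear to respond better, and an arm that starts thinner will appear to respond worse.

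Nothing in the design balances the arms. They are not randomised, and entry allows BMI from above 22 to below 40 kg/m² (Protocol 5.1). The trial is described as a bridging study, and caliper thickness is its only measured efficacy endpoint; the others are ratings or questionnaires. A population difference created or hidden by starting thickness would mislead on a stated objective. As planned, the report would contain no estimate against which to check for this.

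**Working it through.** **Inputs.** n = 10 per arm (SAP section 5) and two-sided alpha 0.05 (SAP section 6). There is no planned figure to reproduce: "No formal sample size calculation was performed", and neither document gives a caliper SD, a target difference or the baseline to Day 84 correlation rho. Rho is therefore an assumption, shown over a range. The SD is assumed equal at both visits, and results are in units of that SD.

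**1. Shift in the change contrast.** Suppose Day 84 = rho × baseline + error, with no arm effect given baseline. A baseline gap d then moves the difference in mean change by (1 − rho) × d in size. For d = 0.5 SD:
- rho 0.5: 0.5 × 0.5 = 0.25 SD
- rho 0.7: 0.3 × 0.5 = 0.15 SD
- rho 0.9: 0.1 × 0.5 = 0.05 SD

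**2. How easily such a gap arises.** If both arms came from one population, the SE of the baseline difference would be √(2/10) = 0.447 SD. The chance of a gap beyond 0.5 SD would be 2 × (1 − Φ(0.5/0.447)) = 0.26. This covers chance imbalance only. It says nothing about a systematic difference between the populations.

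**3. Precision at 10 per arm.**
- Change score: variance = 2(1 − rho) × 2/10, with t on 18 df (critical value 2.101).
- ANCOVA: variance = (1 − rho²) × 2/10 × (1 + 1/16), with t on 17 df (2.110). The term 1/16 is the expected cost of estimating the slope when there is no systematic baseline gap.
- Variance ratio, ANCOVA to change score = (1 + rho)/2 × 1.0625.

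| rho | variance ratio | half-width, change | half-width, ANCOVA | width ratio |
|---|---|---|---|---|
| 0.3 | 0.69 | 1.112 | 0.928 | 0.84 |
| 0.5 | 0.80 | 0.940 | 0.842 | 0.90 |
| 0.7 | 0.90 | 0.728 | 0.695 | 0.95 |
| 0.8 | 0.96 | 0.594 | 0.584 | 0.98 |
| 0.9 | 1.01 | 0.420 | 0.424 | 1.01 |
| 0.95 | 1.04 | 0.297 | 0.304 | 1.02 |

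The interval gain ends where (1 + rho)/2 × 1.0625 × (2.110/2.101)² = 1, at rho of about 0.87.

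A systematic gap reduces the gain. With d = 0.5 SD the expected squared baseline difference is 0.2 + 0.25 = 0.45, so the factor 1.0625 becomes 1 + 0.45/(0.2 × 16) = 1.141. The variance ratios become 0.75 × 1.141 = 0.86 (rho 0.5), 0.85 × 1.141 = 0.97 (rho 0.7) and 0.90 × 1.141 = 1.03 (rho 0.8).

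**4. Bias runs both ways.** The table gives simulated type I error at nominal 5%, with a true population baseline gap of 0.5 SD and 40,000 trials per scenario.

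| rho | change-score test, arms equal given baseline | ANCOVA, arms equal in mean change |
|---|---|---|
| 0.5 | 8.0% | 8.8% |
| 0.7 | 6.9% | 7.0% |
| 0.9 | 5.7% | 5.8% |

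Each method holds about 5% under its own null. With no population gap, both hold about 5%.

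**5. Scale.** At rho 0.5 the shift of 0.25 SD is 0.25/0.940 = 27% of the planned interval's half-width; at rho 0.7 it is 0.15/0.728 = 21%. A true difference of 1 SD of change has 56% power with the planned t-test. The difference detectable with 80% power moves from 1.33 to 1.19 caliper SD at rho 0.5, and from 1.03 to 0.98 at rho 0.7.

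**The case against.** The strongest objection is that ANCOVA is not clearly the better method here. The shift in step 1 takes equality given baseline as the meaning of no difference. In non-randomised groups an equally legitimate null is equal mean change, and under that null ANCOVA is the biased method by almost the same amount. Which contrast a bridging study wants is a choice of estimand that the documents do not make. This stands, and it rules out presenting ANCOVA as a correction of the planned test.

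Three further points also stand:
- Both arms must be grade 3 to 4 on both chin scales, and bulges too large or too small for 32±4 injections are excluded (Protocol 5.1 and 5.2). This limits the spread of baseline fat, though it does not equalise thickness.
- Thickness at screening is tabulated by arm, so a large imbalance would be visible.
- The 26% in step 2 does not show that the planned test is invalid. Under chance imbalance alone, its overall error stays at 5%.

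A reader might infer that the plan ignores baseline thickness. It does not, because the tested variable is the reduction from baseline. A reader might also infer that the unadjusted comparison is bound to be noisier. That depends on rho, which the documents do not give, and at high rho it is false.

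The objection does not defeat reporting a second estimate. Because each method fails under the other's null, the two together say more than either alone.

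**Conclusion.** The point holds in a limited form. The plan uses baseline by subtraction, provides no baseline-adjusted comparison, and so gives the reader no check on whether a difference between two non-randomised groups of 10 reflects starting thickness. For a 0.5 SD baseline gap, and if the arms are equal given baseline, the distortion is 0.25 SD at an assumed rho of 0.5 and 0.15 SD at 0.7. The precision gain is a secondary benefit. It is modest at low to moderate rho, negligible near 0.8, and smaller still if the populations differ systematically at baseline. All these figures rest on assumed rho, equal SDs at the two visits and a linear relation.

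The documents do not support the stronger conclusion that ANCOVA should replace the planned test, or that it would remove confounding. Differences in BMI or in the number of injections would remain after adjustment for thickness.

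Priority is low. The endpoint is exploratory, the primary endpoint is pharmacokinetic, p-values are for trends, and power is limited under either method. The lack of a rule for choosing between the t-test and the rank test is a separate matter that ANCOVA does not settle.

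**What to change.** In SAP section 6, under the caliper endpoint:

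1. Keep the planned change-score comparison. State whether the between-arm reduction is absolute or relative, and report the mean difference with its 95% CI.
2. Pre-specify beside it an ANCOVA of Day 84 thickness (or of absolute change, which gives the same adjusted difference) on arm and screening thickness, reporting the adjusted difference with its 95% CI.
3. State in advance that if the two estimates disagree, baseline imbalance may explain the result, and that neither estimate alone is decisive.

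The cost is a few lines of SAP text and one model on data already collected. The model spends one degree of freedom and assumes a linear relation with a common slope in both arms. Neither the change-score t-test nor the rank test checks that assumption; a plot of Day 84 against screening thickness by arm would let the reader judge it.

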1.2 Schedule of Activities

Study Procedure	Screening Day	Baseline (Treatment)	Visit Schedule (Days 1 to 84)				
Study Day	Day (-28) through Day (-1)	Day 0	Day 1	Day 7	Day 28	Day 56	Day 84
Signed informed consent	X						
Medical history	X						
Physical Exam	X		X	X			X
Concomitant Medication	X	X	X	X	X	X	X
Pregnancy ß-hCG	X						
Pregnancy urine test (women)		X					X
Caliper measurement of submental fat	X				X	X	X
Weight measurements	X	X			X	X	X
Biochemistry Lab parameters	X		X	X	X		X
Pharmacokinetics		X	X				
ECG	X		X				X
Vital signs	X	Pre X post	X	X	X	X	X
Injection of RZL- 012		X					
Clinician Chin Assessment Tool (C-CAT)	X	X			X	X	X
Subject- Self-Chin Assessment Tool (S-CAT)	X	X			X	X	X
Physician Global Assessment Improvement Scale	X				X	X	X

Study Procedure Screening Baseline (Treatment) Visit Schedu			le (Days 1 to 84)				
Study Day	Day (-28) through Day (-1)	Day 0	Day 1	Day 7	Day 28	Day 56	Day 84
(GAIS) and physician global assessment							
Subject's Satisfaction questionnaire for SMF appearance	X				X	X	X
Subject's impact questionnaire	X				X	X	X
Subject Global Assessment of Change and subject self assessment	X				X	X	X
2D Standardized photography	X		X	X	X	X	X
AEs		X	X	X	X	X	X

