8.10 Subject's Satisfaction Questionnaire

Subject's satisfaction questionnaire (yes/no questions) will be conducted by the subjects at screening and on study visits Day 28, Day 56 and Day 84.

Subjects will be asked the following questions and will score their satisfaction based on the grades below:

How satisfied are you currently with the appearance of your chin, neck and jawline area?

Score	Grade
0	Extremely Satisfied
1	Satisfied
2	Somewhat satisfied
3	Neither Satisfied nor Dissatisfied
4	Somewhat Dissatisfied
5	Dissatisfied
6	Extremely Dissatisfied

How happy are you with the appearance of your neck as it relates to your chin fat?

Score	Grade
0	Extremely Satisfied
1	Satisfied
2	Somewhat satisfied
3	Neither Satisfied nor Dissatisfied
4	Somewhat Dissatisfied
5	Dissatisfied
6	Extremely Dissatisfied

How satisfied are you with the result of your treatment*?

Score	Grade			
0	Very satisfied			
1	Satisfied			
2	Somewhat satisfied			
3	Somewhat dissatisfied			
4	Dissatisfied			

5	Very dissatisfied
---	-------------------

How likely would you be to recommend this procedure to friends and family*?

Score	Grade
0	Extremely likely
1	Very likely
2	Somewhat likely
3	A little likely
4	Not at all likely

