• Subject's satisfaction questionnaires answers will be summarized using desciptive statistics by study visit for each study arm. Shift from baseline will be evaluated and tabulated in the same manner.

Two Subject satisfaction binary variables will be defined for every subject in the ITT population based on the satisfaction questionnaire for each one of the questions:

- 1. Subjects who at any point in time answered "Extremely Satisfied" or "Satisfied" (Grades 0,1).
- 2. Subjects who at their last assessment answered "Extremely Satisfied" or "Satisfied" (Grades 0,1).

Subjects with no assessment will be considered as non-responders. The proportion of satisfied subjects (according to said binary variables) will be calculated along with 95% exact confidence intervals for each treatment group. Fisher's Exact test will be applied for testing the statistical significance of the difference in percent of satisfied subjects between treatment groups.

• SMF improvement using Subject's Impact Questionnaire answers will be summarized using descriptive statistics by study visit for each study arm. Shift from baseline will be evaluated and tabulated in the same manner.

Medi Stat	document number: 140-BST-PLN-001	PAGE: 20 of 20
TITLE: Statistical Analysis Plan	of Protocol Number RZL-012-SMFC-P2US-001	EFFECTIVE DATE : 03/08/2022 REVISION NUMBER : 1.0

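### Satisfaction is compared between the two populations only by Fisher's exact test on a grade 0-1 cut, which at 10 per arm is insensitive, makes no use of the screening grade, and as worded can count a screening answer as a response

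*SAP*

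**What the plan says.** The satisfaction questionnaire has four questions (Protocol section 8.10). The first two concern appearance and have seven grades, 0 to 6; the first reads "How satisfied are you currently with the appearance of your chin, neck and jawline area". The third concerns the treatment result and has six grades. The fourth concerns recommending the procedure and has five. The schedule (Protocol section 1.2, row "Subject's Satisfaction questionnaire for SMF appearance") places the questionnaire at screening and on Days 28, 56 and 84.

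In the satisfaction paragraph of SAP section 6, answers and shifts from baseline are tabulated by arm. Two yes/no variables are then formed for each question. One is a grade of 0 or 1 on any occasion. The other is "Subjects who at their last assessment answered 'Extremely Satisfied' or 'Satisfied' (Grades 0,1"). Subjects with no assessment count as non-responders. The between-arm analysis is: "Fisher's Exact test will be applied for testing the statistical significance of the difference in percent of satisfied subjects between treatment groups".

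SAP section 5 gives 10 subjects per arm and says "No formal sample size calculation was performed". It adds: "Any p-value which may be shown in the final report, will be presented only to establish trends". SAP section 6 nevertheless sets a threshold: "All tests will be two-tailed, and a p value of 5% or less will be considered statistically significant". Protocol section 9.5 names no method for these endpoints beyond a two-sided 5% test.

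**The concern.** Three features of this comparison work against its purpose.

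1. **The cut discards order.** A subject who moves from grade 6 to grade 2 counts the same as one who stays at 6. With 10 per arm, what remains is tested by a method that is strongly conservative at this size.
2. **The cut is on the absolute level.** C-CAT and S-CAT responders in the same SAP are defined by improvement from baseline, and caliper reduction is compared on change. Satisfaction is not. The arms are populations, not randomised groups, and entry is restricted on C-CAT and S-CAT grade but not on satisfaction. If the populations use the scale differently at screening and the difference persists, it enters the comparison.
3. **The any-occasion variable does not exclude screening.** Read literally, a subject already satisfied before treatment is a responder. The last assessment could also be the screening one if no later visit took place.

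At stake is a supporting result in a bridging study. The test could miss a real difference between populations, or show one where both improved equally.

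**Working it through.** **Inputs.** From the documents: 10 per arm, two-sided 5%, the grade 0-1 cut, seven grades for questions 1 and 2. The documents give no satisfaction rates, SD, effect or screening-to-follow-up correlation, so there is no plan figure to reproduce. Everything on those quantities below is assumed.

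**Step 1: Fisher's test at 10 vs 10, by enumerating all 11 x 11 tables.** It rejects for 0 vs 5 or more, 1 vs 7 or more, 2 vs 8 or more, 3 vs 9 or more, and 4 or 5 vs 10. The largest true size over all common rates is 1.28%, at a rate of 0.5. Exact power, with the usual asymptotic two-proportion formula for comparison:

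| Satisfied rates | Fisher, exact | Asymptotic formula |
|---|---|---|
| 0.3 vs 0.8 | 43% | 63% |
| 0.2 vs 0.8 | 64% | 82% |
| 0.5 vs 0.9 | 30% | 50% |
| 0.7 vs 0.9 | 6% | 19% |

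The gap between columns shows that some of the weakness comes from Fisher's conservatism and not from the cut.

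**Step 2: what a rank test would gain.** A seven-grade score is cut from a latent normal with a between-population shift of d SD. With 30% satisfied in the reference arm, the other arm's rate is Φ(Φ⁻¹(0.3) + d), for example 0.68 at d = 1. Simulated power (10,000 trials per setting), with the change-score columns by assumed screening-to-follow-up correlation ρ:

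| d | Fisher | Rank, grade | Change, ρ = 0 | Change, ρ = 0.5 | Change, ρ = 0.7 |
|---|---|---|---|---|---|
| 0.3 | 2% | 8-9% | 6% | 8% | 11% |
| 0.5 | 5% | 16% | 10% | 16% | 21% |
| 1.0 | 21-22% | 48-50% | 28% | 45% | 59% |
| 2.0 | 74-75% | 96-97% | 65% | 84% | 92% |

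Over the assumed reference rates (0.1 to 0.7), the gain of the rank test on the grade over Fisher is about 6 points at 0.3 SD, 10-12 at 0.5 SD, 27-38 at 1 SD, 30-53 at 1.5 SD and 17-40 at 2 SD. With no difference, the rank test (tie and continuity correction) rejects in 4.4% of runs.

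**Step 3: a screening gap that carries over.** Assume screening means of 4.2 and 5.2 (SD 0.7) and the same improvement in both arms (mean 3 grades, SD 1). Expected responder rates are 59% and 29%, with mean changes of -2.9 and -3.0. Fisher rejects in about 13% of trials; a rank test on change in 4-5%. The gap is 1/0.7 = 1.4 SD, which is large. With half a grade, Fisher rejects in 3.7%, below nominal. On a latent scale with full carry-over and equal change, Fisher rejects in about 5% at 0.5 SD, 18-22% at 1 SD and 38-51% at 1.5 SD.

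**Step 4: a screening gap that does not carry over.** With the one-grade gap at screening but equal follow-up distributions, Fisher rejects in about 1% of trials and the rank test on change in about 22% (20-27% in nearby settings). On the latent scale, if a 1 SD gap shrinks in line with ρ (0.3 to 0.7), Fisher rejects in 2-10% and a change test in 13-25%. ANCOVA on the screening grade holds about 5% in that case, but rejects in 12-27% when a 1 SD gap carries over fully. No single test covers both cases.

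**Step 5: screening answers counted as responses.** Let 30% of each arm be satisfied after treatment, none of arm A at screening, and a fraction q of arm B at screening, independently. Arm B's any-occasion rate is 1 - 0.7 x (1 - q).

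| q | Arm B rate | Fisher rejects |
|---|---|---|
| 0.2 | 0.44 | 3% |
| 0.3 | 0.51 | 6% |
| 0.4 | 0.58 | 11% |
| 0.5 | 0.65 | 18% |

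**The case against.** The strongest reply is that little rests on this test. The primary endpoint is PK, and the sample size statement speaks only to that: "The planned sample size of 10 subjects per study arm is sufficient to compare the PK profile between the 2 study populations". Satisfaction is among the additional exploratory endpoints, p-values are for trends, and the SAP already plans summaries by visit, shift tables and proportions with exact intervals. This stands, and it sets the priority. It does not remove the point: an indicator of trend still needs some sensitivity, and the 5% significance threshold still applies to this test.

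Several stronger readings are tempting and are not supported:

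- **A fixed loss of about 30 points.** This holds only near a 1 SD shift. The documents supply no distribution from which to choose a shift, and part of the loss is Fisher's conservatism.
- **A baseline difference reported as a treatment difference.** Both arms receive the same treatment (Protocol section 4.2). The contrast is between populations.
- **The screening answer is ignored.** It is tabulated as a shift; it is only absent from the test as an adjustment. For questions 3 and 4 a meaningful screening answer may not exist.
- **A seven-grade scale throughout.** Only questions 1 and 2 have seven grades.
- **A change score as the cure.** Step 4 shows that it can create the false difference it is meant to prevent.

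A large share of subjects at grade 0-1 at screening may also be unlikely in people who seek fat reduction with S-CAT grade 3 or 4. The criteria do not exclude it.

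**Conclusion.** The point holds as a low-priority improvement. From the documents alone: Fisher's test on an absolute cut is the only named between-arm satisfaction test, its true size at 10 per arm is at most 1.3%, and the any-occasion wording admits a screening answer. Under assumed distributions, a rank test on the grade adds between about 6 points of power (0.3 SD) and 30-53 points (1.5 SD). The risk from a screening gap is conditional: it needs a sizeable gap that persists to follow-up, about 13% rejections for a 1.4 SD gap and under 4% for half that. A reader might infer that the planned result would be misleading in general. The documents do not support that, since neither the size nor the persistence of a screening gap is known.

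**What to change.** In the satisfaction paragraph of SAP section 6:

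- Replace Fisher's test by an exact Wilcoxon-Mann-Whitney comparison of the Day 84 grade for each question, with the Hodges-Lehmann difference and 95% CI.
- For questions 1 and 2, report the same comparison of change from screening, and state that the two are read together. The Day 84 comparison does not remove a gap that carries over, and being more sensitive than Fisher's test it will pick one up more often. The change comparison removes a gap only if it does carry over.
- Restrict both yes/no variables to post-treatment visits. Keep their proportions with exact CIs as descriptive output, without a p-value.
- Carry the missing-data rule over to the rank tests: for example, the last post-treatment grade if Day 84 is missing, and the worst rank if there is no post-treatment assessment.

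The cost is SAP wording and a short programming change, with no new data, visits or subjects. The number of tests falls from 2 x 4 = 8 to 4 + 2 = 6. The downsides are that a rank result is harder to state than percent satisfied, and that the change comparison can have less power than the grade comparison when the screening correlation is low (28% against about 49% at 1 SD and zero correlation). The power figures in the working are simulated; the exact version may differ slightly because of ties.
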